# General PK Parameter Rules

- Actual PK sampling times will be used in the final analyses of individual PK parameters, except for non-bolus pre-dose sampling times which will be set to zero.
- Cmax and tmax will be reported from observed values. If Cmax occurs at more than one time point, tmax will be assigned to the first occurrence of Cmax.

- AUC parameters will be calculated using a combination of the linear and logarithmic trapezoidal methods (linear-log trapezoidal rule). The linear trapezoidal method will be applied up to  $t_{max}$  and then the logarithmic trapezoidal method will be used after  $t_{max}$ .
- The minimum requirement for the calculation of AUC will be the inclusion of at least three consecutive serum concentrations above the lower limit of quantification (LLOQ), with at least one of these concentrations following  $C_{max}$ .
- AUC(0-∞) values where the percentage of the total area extrapolated is more than 20% will be flagged. Any AUC(0-∞) value excluded from summary statistics will be noted in the footnote of the summary table. If AUC(0-∞) cannot be determined for all subjects an alternative AUC measure, such as AUC to a fixed time point, may be used in the assessment exposure between dose groups.
- Half-life  $(t_{1/2})$  will be calculated, when appropriate, based on the apparent terminal log-linear portion of the concentration-time curve. The start of the terminal elimination phase for each subject will be defined by visual inspection and generally will be the first point at which there is no systematic deviation from the log-linear decline in serum concentrations. Half-life will only be calculated when a reliable estimate for this parameter can be obtained comprising of at least 3 data points. If  $t_{1/2}$  is estimated over a time window of less than 2 half-lives, the values will be flagged in the data listings. Any  $t_{1/2}$  value excluded from summary statistics will be documented in the footnote of the summary table.
- A uniform weighting scheme will be used in the regression analysis of the terminal log-linear portion of the concentration-time curve.
- The parameters based on the last predicted quantifiable drug concentration (Clast) will be reported.

# Individual PK Parameter Rules

- Only quantifiable concentrations will be used to calculate PK parameters with the exception of special handling of certain concentrations reported below the lower limit of quantitation (BQL). Serum concentrations reported as BQL will be set to a value of zero when all of the following conditions are met:
  - The compound is non-endogenous.
  - The samples are from the initial dose period for a subject or from a subsequent dose period following a suitable wash-out period.
  - $\circ$  The time points occur before the first quantifiable concentration.
- All other BQL concentrations that do not meet the above criteria will be set to missing.

• Also, where two or more consecutive concentrations are BQL towards the end of a profile, the profile will be deemed to have terminated and therefore any further quantifiable concentrations will be set to missing for the calculation of the PK parameters unless it is considered to be a true characteristic of the profile of the drug.

# **Individual Concentration vs. Time Profiles**

- Individual concentrations will be plotted utilizing actual sampling times.
- The terminal point selections will be indicated on a semi-logarithmic plot.

#### **Average Concentration vs. Time Profiles**

- The average concentration profiles will be graphed using scheduled (nominal) sampling times.
- The average concentration profiles will be graphed using arithmetic average concentrations.
- The pre-dose average concentration for single-dose data from non-endogenous compounds will be set to zero. Otherwise, only quantifiable concentrations will be used to calculate average concentrations.
- Concentrations at a sampling time exceeding the sampling time window specified in the protocol, or  $\pm 10\%$ , will be excluded from the average concentration profiles.
- Concentrations excluded from the mean calculation will be documented in the final study report.
- A concentration average will be plotted for a given sampling time only if 2/3 of the individual data at the time point have quantifiable measurements that are within the sampling time window specified in the protocol or ± 10%. An average concentration estimated with less than 2/3 but more than 3 data points may be displayed on the mean concentration plot if determined to be appropriate and will be documented within the final study report.

#### **Treatment of Outliers during Pharmacokinetic Analysis**

Application of this procedure to all PK analyses is not a requirement. Rather, this procedure provides justification for exclusion of data when scientifically appropriate. This procedure describes the methodology for identifying an individual value as an outlier for potential exclusion, but does not require that the value be excluded from analysis. The following methodology will not be used to exclude complete profiles from analysis.

#### Data within an Individual Profile

A value within an individual profile may be excluded from analysis if any of the following criteria are met:

- For PK profiles during single dosing of non-endogenous compounds, the concentration in a pre-dose sample is quantifiable.
- For any questionable datum that does not satisfy the above criteria, the profile will be evaluated and results reported with and without the suspected datum.

### Data between Individual Profiles

- 1. If n<6, then the dataset is too small to conduct a reliable range test. Data will be analyzed with and without the atypical value, and both sets of results will be reported.
- 2. If  $n \ge 6$ , then an objective outlier test will be used to compare the atypical value to other values included in that calculation:
  - a. Transform all values in the calculation to the logarithmic domain.
  - b. Find the most extreme value from the arithmetic mean of the log transformed values and exclude that value from the dataset.
  - c. Calculate the lower and upper bounds of the range defined by the arithmetic mean  $\pm 3$ \*SD of the remaining log-transformed values.
  - d. If the extreme value is within the range of arithmetic mean  $\pm 3$ \*SD, then it is not an outlier and will be retained in the dataset.
  - e. If the extreme value is outside the range of arithmetic mean  $\pm 3$ \*SD, then it is an outlier and will be excluded from analysis.

If the remaining dataset contains another atypical datum suspected to be an outlier and  $n \ge 6$  following the exclusion, then repeat step 2 above. This evaluation may be repeated as many times as necessary, excluding only one suspected outlier in each iteration, until all data remaining in the dataset fall within the range of arithmetic mean  $\pm 3$ \*SD of the log-transformed values.

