# 9. STATISTICAL METHODOLOGY

#### 9.1 General

Data listings will be provided for all data that is collected and added to the database. Summary statistics and statistical analysis will only be presented for data where detailed in this SAP. For continuous data, summary statistics will include the arithmetic mean, arithmetic standard deviation (SD), median, min, max and number of subjects (N); for log-normal data (e.g. the PK parameters: area under the concentration versus time curve [AUC] and maximum observed drug concentration [ $C_{max}$ ]) the geometric mean and geometric percent coefficient of variation (CV%) will also be presented. For categorical data, frequency count and percentages will be presented. Data listings will be provided for all subjects up to the point of withdrawal, with any subjects excluded from the relevant population highlighted. Summary statistics and statistical analyses will generally only be performed for subjects included in the relevant analysis population. For the calculation of summary statistics and statistical analysis, unrounded data will be used.

Mean change from baseline is the mean of all individual subjects' change from baseline values. Each individual change from baseline will be calculated by subtracting the individual subject's baseline value from the value at the timepoint. The individual subject's change from baseline values will be used to calculate the mean change from baseline using a SAS procedure such as Proc Univariate. For vital signs and immunogenicity, baseline is defined as Day 1 predose.

Data analysis will be performed using SAS® Version 9.4 or greater.

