#### Reporting of Excluded Values

Individual values excluded as outliers will be documented in the final report. Approval of the final report will connote approval of the exclusion.

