#### 9.3.2 Pharmacokinetic Statistical Methodology

The PK parameter estimates for galcanezumab will be listed and summarized using appropriate descriptive statistics and figures. In addition, summary and individual figures of serum concentrations of galcanezumab will be produced.

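### The SAP's outlier rule contradicts itself on exclusion, and at the planned group sizes it can drop genuine Cmax and AUC values with no all-data summary promised

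*SAP*

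**What the plan says.** SAP 9.3.1 handles PK outliers under four subheadings.

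- **Treatment of Outliers during Pharmacokinetic Analysis** makes the procedure optional. It identifies a value for possible exclusion "but does not require that the value be excluded from analysis".
- **Data within an Individual Profile** covers a questionable point inside one subject's profile: the profile is evaluated and "results reported with and without the suspected datum".
- **Data between Individual Profiles** splits by group size. For n<6, "Data will be analyzed with and without the atypical value, and both sets of results will be reported". For n≥6, "an objective outlier test will be used to compare the atypical value to other values included in that calculation": values are logged, the most extreme is set aside, and mean ±3 SD is computed from the rest. If the extreme value lies outside that range, "then it is an outlier and will be excluded from analysis". The test may be repeated while n≥6.
- **Reporting of Excluded Values**: "Individual values excluded as outliers will be documented in the final report".

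SAP 9.3.2 adds: "The PK parameter estimates for galcanezumab will be listed and summarized using appropriate descriptive statistics and figures". For log-normal parameters such as AUC and Cmax, SAP 9.1 says that "the geometric mean and geometric percent coefficient of variation (CV%) will also be presented". Protocol Section 4 makes Cmax and AUC(0-∞) the primary endpoints.

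**The concern.** There are three difficulties.

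1. **The texts disagree.** The preamble leaves exclusion open after a value has been identified; step 2e makes it automatic. Two analysts following the same SAP could report different primary summaries from the same data.
2. **The safeguard is missing where this trial will operate.** Groups of 8 to 12 fall under the n≥6 branch, the only between-profile branch without a promise to report both ways.
3. **The trigger and the limit are weak.** An atypical value is not defined, so whether to test is decided with the data in view. The ±3 SD range is estimated from only 7 to 11 values after the most extreme one has been removed, so it excludes genuine values much more often than the multiplier suggests.

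The primary endpoints are reported only descriptively, and the rule names no parameter, so it can reach both. If a genuine tail value is dropped, the geometric CV% is too small and exposure in Chinese subjects looks more uniform than it was.

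**Working it through.** **Inputs**

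- Galcanezumab group size: 8 completers per dose (Protocol 5.2 and 10.1). Up to 15 per cohort at 4:1 gives 15 × 4/5 = 12 enrolled. The PK set requires a dose but not completion (SAP 8), so n can run from 8 to 12.
- Rule: steps 2a to 2e, repeated while n≥6.
- Scale: 34% inter-individual variability, given for apparent clearance in Protocol 3.2.1.1. It is assumed here for Cmax and AUC. Log-SD = √ln(1 + 0.34²) = 0.331.

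The documents give no false-exclusion rate for the rule, so there is no figure of theirs to reproduce.

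**Rate if every group is tested (clean log-normal data)**

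On the log scale, a value minus the mean of the other n−1 values has variance σ²(1 + 1/(n−1)). Divided by the SD of those others, it equals √(1 + 1/(n−1)) times a t variable on n−2 df. A value is therefore flagged when |t| on n−2 df exceeds 3/√(1 + 1/(n−1)). The group rate is at most n times the per-value probability p.

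| n | t limit | df | p per value | n × p | simulated, with iteration |
|---|---|---|---|---|---|
| 8 | 2.806 | 6 | 0.0309 | 24.7% | 24.7% |
| 10 | 2.846 | 8 | 0.0216 | 21.6% | 21.8% |
| 12 | 2.872 | 10 | 0.0166 | 19.9% | 19.8% |

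The simulation used 200,000 groups per n. These rates do not depend on the CV. For comparison, with a known mean and SD, ±3 SD would flag 0.27% of values, or 8 × 0.27% = 2.2% of groups of 8. Through the repeat step, two or more genuine values go in 6.8% (n=8) to 4.1% (n=12) of groups.

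**Rate if only atypical values are tested**

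The term is undefined, so a trigger has to be assumed: the value lies at least k-fold from the group geometric mean.

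| Trigger | CV | n=8 | n=12 |
|---|---|---|---|
| ≥1.5-fold | 34% | 23% | 20% |
| ≥2-fold | 34% | 9% | 12% |
| ≥2.5-fold | 34% | 2% | 3% |
| ≥2-fold | 25% | 2% | 3% |
| ≥2-fold | 45% | 18% | 18% |

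**Effect on the reported summaries (CV 34%)**

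| Quantity | n=8 | n=12 |
|---|---|---|
| Routine use: average log-variance too small by | 17% | 11% |
| Routine use: mean geometric CV over all groups | 33.0% → 29.0% | 33.3% → 31.0% |
| Routine use: median geometric CV in affected groups | 32% → 17% | 33% → 22% |
| Routine use: median shift of geometric mean in affected groups, either direction | 9.5% | 7% |
| ≥2-fold trigger: average log-variance too small by | 9% | 8% |
| ≥2-fold trigger: median geometric CV in affected groups | 41% → 25% | 37% → 26% |

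The average bias of the geometric mean is below 0.02%, as a symmetric log-scale model implies.

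**The case against.** The strongest reply is that 20–25% is a worst case the SAP does not intend. The preamble says that the procedure need not be applied to every analysis and is for use where scientifically appropriate, and step 2 concerns an atypical value. At CV 34%, about 62% of first flags at n=8 and 39% at n=12 are less than 2-fold from the geometric mean, and a pharmacokineticist might never test them. This stands: the figure is an upper bound and the documents do not fix the actual rate. But it follows from leaving the trigger undefined, and the rate is still 9% to 12% with a 2-fold trigger.

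Second, the two passages can be read together: the choice to test is optional, and step 2e binds once the test is run. That reading is possible, but the preamble's disclaimer is about excluding a value already identified, which is exactly what step 2e makes automatic.

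Third, exclusions would be visible. They are documented in the report, PK parameters are listed, and under General PK Parameter Rules an excluded AUC(0-∞) value is footnoted on the summary table. With 8 to 12 subjects a reader could recompute if the listings keep the value. This reduces the harm, but none of these provisions promises the all-data summary.

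Fourth, the trial has no hypothesis test and the geometric mean is unbiased on average. That limits the seriousness. However, the descriptive summaries are the trial's primary result, and the CV% is part of them.

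**Conclusion.** The concern holds and should be fixed. The preamble and step 2e need to be reconciled, and the n≥6 branch, which governs both galcanezumab groups, lacks the dual reporting that the SAP promises for n<6 and for questionable points within a profile.

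On clean log-normal data, at least one genuine value is lost in up to 25% (n=8) or 20% (n=12) of groups per parameter. Under a 2-fold trigger the range is 2% to 18% for CVs of 25% to 45%. The understatement of CV% is modest on average, about 2 to 4 percentage points under routine use at CV 34%, but cuts the figure by one-third to one-half in an affected group.

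The upper bound assumes log-normality, testing of every group and removal of every flagged value. The CV figures also assume that the 34% for clearance carries over to Cmax and AUC. The contradiction and the reporting gap depend on none of these assumptions.

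**What to change.** In step 2e, replace the exclusion clause with wording such as: *the value will be flagged; the summary of all data is primary, and results will be reported with and without the flagged value.* This agrees with the preamble and extends the n<6 reporting rule to every n. A value with a documented assay or dosing error can still be handled on that ground, because the change concerns values flagged by the statistical test alone.

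Changing the multiplier is optional and unnecessary once both results are shown. For scale, holding the chance of any false flag near 5% per clean group would need limits of about 4.4 SD at n=8, 4.0 at n=10 and 3.9 at n=12.

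The cost is one or two sentences in the SAP and one extra summary row when a value is flagged. The reported CV% may be slightly larger.

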#### Reporting of Excluded Values

Individual values excluded as outliers will be documented in the final report. Approval of the final report will connote approval of the exclusion.

#### 9.3.2 Pharmacokinetic Statistical Methodology

The PK parameter estimates for galcanezumab will be listed and summarized using appropriate descriptive statistics and figures. In addition, summary and individual figures of serum concentrations of galcanezumab will be produced.

### 9.4 Safety and Tolerability Assessments

#### 9.4.1 Adverse events

Where changes in severity are recorded in the Case Report Form (CRF), each separate severity of the AE will be reported in the listings, only the most severe will be used in the summary tables. A pre-existing condition is defined as an AE that starts before the subject has provided written informed consent and is ongoing at consent. A non-treatment emergent AE is defined as an AE which starts after informed consent but prior to dosing. A treatment-emergent AE is defined as an AE which occurs postdose or which is present prior to dosing and becomes more severe postdose.

All AEs will be listed. Treatment-emergent AEs will be summarized by treatment, severity and relationship to the study drug. The frequency (the number of AEs, the number of subjects experiencing an AE and the percentage of subjects experiencing an AE) of treatment-emergent AEs will be summarized by treatment, Medical Dictionary for Regulatory Activities (MedDRA) version 20.1 (or later) system organ class and preferred term. The summary and frequency AE tables will be presented for all causalities and those considered related to the study drug. Any serious AEs will be tabulated.

#### 9.4.2 Concomitant medication

Concomitant medication will be coded using the WHO drug dictionary (Version September 2017). Concomitant medication will be listed.

# 9.4.3 Clinical laboratory parameters

All clinical chemistry and hematology data will be summarized by parameter and treatment, and listed. Urinalysis data will be listed. Additionally clinical chemistry, hematology and urinalysis data outside the reference ranges will be listed.

Values for any clinical chemistry, hematology and urinalysis values outside the reference ranges will be flagged on the individual subject data listings.

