|--|------------------|----------------|----------------|----|----|----|-----|-----|-----|-----|-----|-----|-----|------|------|------|------|------|------------------|---|
| Day ^a | SCR ^b | - 1 | 1 | 2 | 3 | 5 | 6 | 8 | 10 | 12 | 15 | 22 | 29 | 43 | 57 | 71 | 85 | 113 | 141 ^c | |
| Visit Window (days) | | | | | | | | | | | ±1 | ±2 | ±2 | ±3 | ±3 | ±3 | ±3 | ±3 | ±3 | |
| CRU admission/visits ^d | X | Inpatient stay | | | | | X | X | X | X | X | X | X | X | X | X | X | X | X | X |
| Randomization | | | X | | | | | | | | | | | | | | | | | |
| Study drug injection | | | X ^e | | | | | | | | | | | | | | | | | |
| Informed Consent | X | | | | | | | | | | | | | | | | | | | |
| Eligibility assessment | X | | | | | | | | | | | | | | | | | | | |
| Medical history | X | | | | | | | | | | | | | | | | | | | |
| Recording of AEs ^f | X | X | X | X | X | X | X | X | X | X | X | X | X | X | X | X | X | X | X | |
| Concomitant medication | X | X | X | X | X | X | X | X | X | X | X | X | X | X | X | X | X | X | X | |
| Physical exam ^g | X | X | Predose | | X | | | X | | | X | | X | X | X | | X | X | | |
| Body temperature | X | | | | | | | | | | | | | | | | | | | |
| Height, weight ^h | X | | Predose | | | | | | | | | | | | | | | | X | |
| Vital signs (hours) ⁱ | X | | Predose, 8 | 24 | X | X | X | X | X | X | X | X | X | X | X | X | X | X | X | |
| Single 12-lead ECG (hours) | X | X | | 24 | | | | | | | | | | | | | | X | X (ED only) | |
| Clinical Laboratory tests | X | X | Predose | | | | | | | | X | | | | X | | | X | X (ED only) | |
| Serology: HIV, HBV, HCV | X | | | | | | | | | | | | | | | | | | | |
| Urine drug screen, ethanol breath test ^j | X | X | | | | | | | | | | | | | | | | | | |
| Chest x-ray and T-SPOT test | X | | | | | | | | | | | | | | | | | | | |
| Pregnancy test ^k | X | X | | | | | | | | | | | | | | | | | X | |
| Galcanezumab PK blood sampling (hours) ^l | | | 8 | 24 | 48 | 96 | 120 | 168 | 216 | 264 | 336 | 504 | 672 | 1008 | 1344 | 1680 | 2016 | 2688 | 3360 | |
| PGx blood sampling | | | Predose | | | | | | | | | | | | | | | | | |
| Immunogenicity blood sampling ^m | | | Predose | | | | | | | | X | | X | | X | | X | | X | |

Abbreviations: AE = adverse event; CRU = clinical research unit; ECG = electrocardiogram; ED = early discontinuation; HBV = hepatitis B virus; HCV = hepatitis C virus; HIV = human immunodeficiency virus; PK = pharmacokinetics; PGx = pharmacogenetics; SCR = screening; T-SPOT = T-SPOT® tuberculosis test.

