6.1. Inclusion Criteria

Subjects are eligible for inclusion in the study only if they meet all of the following criteria at screening and/or admission:

[1] are native Chinese (all 4 biological grandparents and both biological parents to be of Chinese origin)

[2] are overtly healthy males or females, as determined by medical history and physical examination

[2a] female subjects:

All females must test negative for pregnancy at the time of enrollment based on a serum pregnancy test and females of childbearing potential must agree to use a reliable method of birth control during the study as well as for 5 months after dosing. Acceptable methods of birth control for this study include oral contraceptives, implantable contraceptives, injectable contraceptives, a contraceptive patch, barrier methods (such as diaphragms with contraceptive jelly, cervical caps with contraceptive jelly, condoms with contraceptive foam, or intrauterine devices), or a partner with vasectomy. Birth control is not required if the female is infertile due to surgical sterilization (hysterectomy, or at least 6 weeks after surgical bilateral oophorectomy or tubal ligation) confirmed by medical history or menopause. Menopause is defined as spontaneous amenorrhea for at least 12 months not induced by a medical condition, or spontaneous amenorrhea of 6-12 months and a follicle-stimulating hormone level >40 mIU/mL.

[3] are at least 18 years old, at the time of screening

[4] have a body mass index (BMI) between 18.5 and 35.0 kg/m², inclusive, at screening

[5] have clinical laboratory test results within normal reference range for the population or investigative site, or results with acceptable deviations that are judged to be not clinically significant by the investigator

- [6] have venous access sufficient to allow for blood sampling as per the protocol
- [7] are reliable and willing to make themselves available for the duration of the study and are willing to follow study procedures
- [8] are able and willing to sign the informed consent form (ICF)

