#### 9.4.4 Vital signs

Vital signs data will be summarized by treatment together with changes from baseline, where baseline is defined as Day 1 predose. Figures of mean vital signs and mean changes from baseline profiles by treatment will be presented by treatment.

Furthermore, values for individual subjects will be listed.

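### Does the SAP need a laboratory baseline and a change-from-baseline or shift summary to tell new laboratory abnormalities from old ones?

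*SAP*

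**What the plan says.** SAP 9.4.3 plans a descriptive summary for two laboratory panels: "All clinical chemistry and hematology data will be summarized by parameter and treatment, and listed". Urinalysis is listed only. For abnormal values it adds: "Additionally clinical chemistry, hematology and urinalysis data outside the reference ranges will be listed". Out-of-range values are also flagged in the individual subject listings. The section names no baseline, no change from baseline and no shift table.

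The neighbouring section differs: "Vital signs data will be summarized by treatment together with changes from baseline, where baseline is defined as Day 1 predose" (SAP 9.4.4). SAP 9.1 is consistent with that: "For vital signs and immunogenicity, baseline is defined as Day 1 predose". It also sets a scope rule: "Summary statistics and statistical analysis will only be presented for data where detailed in this SAP".

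For adverse events the SAP does separate new from old: "A treatment-emergent AE is defined as an AE which occurs postdose or which is present prior to dosing and becomes more severe postdose" (SAP 9.4.1).

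In the protocol, the Schedule of Activities (Section 2) has the laboratory row "Clinical Laboratory tests | X | X | Predose", followed by Days 15, 57 and 113 and an early-discontinuation sample. Inclusion criterion [5] accepts subjects with normal laboratory results, or with "results with acceptable deviations that are judged to be not clinically significant by the investigator". Protocol 10.3.2.2 names laboratory parameters and vital signs as the safety parameters, asks for listings and standard descriptive statistics, and provides for further analysis if review of the data warrants it.

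**The concern.** Four features together suggest an oversight.

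- Protocol 10.3.2.2 puts laboratory values and vital signs side by side, yet only vital signs get a within-subject summary.
- There are three predose samples (screening, Day -1, Day 1 predose), and none is named as the reference.
- Criterion [5] lets pre-existing out-of-range values into the study.
- SAP 9.1 can be read as ruling out any table that the SAP does not spell out.

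On that reading, no planned group table would show by treatment which postdose laboratory abnormalities arose after dosing. Those that the investigator did not report as adverse events would go uncounted, and an abnormality already present at entry could be mistaken for a drug effect, or the reverse.

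**Working it through.** The plan gives no figure for this point, so the check compares the texts and then sizes what is absent.

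**1. Does the SAP fall short of the protocol?** Protocol 10.3.2.2 asks for listings and standard descriptive statistics. SAP 9.4.3 lists all laboratory data and summarizes chemistry and hematology by treatment. The request is met and nothing is contradicted.

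**2. Is a definition missing?** A baseline is an input to a change score or a shift. SAP 9.4.3 plans neither, so no planned laboratory analysis lacks an input. The absent baseline follows from the absent change summary and is not a second gap.

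**3. Does SAP 9.1 block further tables?** Its scope rule concerns data that the SAP details, and laboratory data are detailed in 9.4.3. SAP Section 3 allows supplementary analyses if they are identified in the study report, and Protocol 10.3.2.2 provides for them if warranted.

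**4. Can new be told from old?** The schedule gives 3 predose draws, 3 scheduled postdose draws and 1 early-discontinuation draw, 7 in all. Without screening that leaves 6, which matches the 6 clinical laboratory samples in Protocol Appendix 4. Each flagged postdose value can therefore be set against that subject's own predose values in the listings.

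**5. Is there a route to a group table?** Protocol Appendix 1 counts an abnormal laboratory finding as a possible adverse event. Protocol 9.2 makes the investigator document review of every laboratory report, and Protocol 7.3 keeps site staff blinded. Under Protocol 9.5.8 the sponsor physician reviews laboratory analytes. SAP 9.4.1 then tabulates treatment-emergent events by treatment.

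**6. How many values might pre-date dosing?** The documents give no rates, so these are assumptions: a normally distributed analyte, symmetric limits, and 5% or 1% out of range per visit. With p the rate per direction (0.025 or 0.005), z the matching limit and no drug effect, the share of postdose out-of-range values already out in the same direction at predose is P(pre > z and post > z)/p:

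| Within-subject correlation | 0.3 | 0.5 | 0.7 | 0.8 | 0.9 |
|---|---|---|---|---|---|
| 5% out of range | 10% | 19% | 33% | 44% | 59% |
| 1% out of range | 4% | 10% | 23% | 34% | 51% |

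The range is wide and depends wholly on the assumptions. It shows that old abnormalities may be common, not that the plan mishandles them.

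**7. What would a shift table hold?** At 5% and correlation 0.5, about 4.1% of subjects move from normal to out of range at a given visit by chance, and 4.1% move back. At full enrollment of 30 and 4:1, placebo has 30/5 = 6 subjects and each dose has 15 × 4/5 = 12.

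- Expected shifts per analyte and visit: 6 × 0.041 = 0.25 on placebo; 12 × 0.041 = 0.49 per dose.
- Chance that a cell holds 0 or 1 on placebo: 0.959^6 + 6 × 0.041 × 0.959^5 = 0.778 + 0.200 = 0.98.
- The same per dose: 0.959^12 + 12 × 0.041 × 0.959^11 = 0.605 + 0.310 = 0.92.

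Protocol Appendix 2 lists 13 numeric hematology and 11 chemistry analytes. With 3 visits and 3 treatments that makes 24 × 3 × 3 = 216 such cells, nearly all 0 or 1.

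**8. Would change from baseline do it?** No. A mean change does not classify any value as new or old. Its standard error relative to the observed value is sqrt(2(1 - rho)): 1.18 at correlation 0.3, 1.00 at 0.5, 0.77 at 0.7. It is noisier than the observed value when the correlation is below 0.5.

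**The case for a change.** The strongest reply is that a listing is not a summary. At an assumed 5% rate, 24 analytes × 3 visits × 30 subjects × 0.05 gives about 108 postdose out-of-range values, and sorting them into new and old by hand yields no count by treatment. The clauses that permit added analyses depend on someone first noticing a signal. With no reference named in advance, the baseline for any added table would be chosen after the data are seen. Day 1 predose is already the reference for vital signs, so naming it for laboratory data would cost little.

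The facts in this stand: the SAP text names no laboratory baseline, does not say that summaries are by time point, and plans no count of new abnormalities. They describe a preference about presentation. About 108 values is 3.6 per subject, which can be read against that subject's predose results. A baseline chosen late would affect only an unplanned descriptive table.

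The contrast with vital signs also weakens on inspection. Vital signs have 17 scheduled postdose time points, which suit mean-change profiles; laboratory tests have three. A different presentation is not an inconsistency.

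**Conclusion.** The concern does not hold. SAP 9.4.3 delivers what Protocol 10.3.2.2 asks for, and no stated rule, figure or analysis is wrong. The secondary endpoint is the incidence of adverse events and serious adverse events, the primary endpoints are pharmacokinetic, and SAP 9.4.9 plans no safety inference. No endpoint, error rate or sample size is touched. What no group summary in the SAP text counts is postdose abnormalities not reported as adverse events, in at most about 30 subjects, and these remain visible in the flagged listings. A shift table would add cells with about 0.25 (placebo) or 0.5 (each dose) expected events and would mostly repeat the listings.

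Those sizes rest on an assumed 5% out-of-range rate, a correlation of 0.5 and full enrollment; the textual conclusion does not. SAP Section 3 places the detailed table descriptions in a separate shell document that was not available, so it is not known whether the planned tables already show time points or changes. The conclusion is the same either way.
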